4.1 Inclusion Criteria

- Males and females 18-64 years old
- have had spinal cord injury for more than one year
- have injury level at T10 or above
- not ambulatory and use a wheelchair for mobility
- non smokers or able to refrain from smoking four hours prior to and during the study

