6.0 Study Design and Procedures

Study Design. This study uses a repeated measures design, and each subject will act as his/her own control. Each subject will undergo the two protocols in the experimental procedures: AP protocol and Control protocol. To ensure the order of the two protocols are randomized, the order of AP and Control protocols will be determined by drawing one envelope from the envelope pool. We will start with a pool of total 20 envelopes (10 envelopes indicating AP protocol first, and 10 envelopes indicating control protocol first). Once the envelope is drawn from the pool, it will not return to the pool.

Study Procedures (Research purpose). After enrollment, subjects will proceed to the following procedures: 1) experimental procedures, 2) vascular control measures, 3) pressure mapping of wheelchair and 4) blood withdraw.

1) **Experimental procedure (approximately 4.5 hours)**

Each subject will undergo two study protocols: AP and control (figure 1), and the order of the protocols will be randomized as described previously. A 30-minute washout period will be provided in between the two protocols. Two Laser Doppler flowmetry (LDF) flat probes (moor instrument, Wilmington, DE) will be taped to the sacrum and one heel to collect the skin blood flow response throughout both AP and control protocols. A whole body pressure mapping system (Xsensor, Xsensor Technology Corp., Alberta, Canada) will be used between the subject and the overlay to collect the inter pressure data. For the AP cycle, we will use four 10-minute cycles (5 minutes of high pressure and 5 minutes of low pressure).

AP protocol: The subject will first lie on his/her side quietly for 10 minutes to collect the baseline skin blood flow, followed by lying supine on the Dabir AP overlay for 40 minutes, and then side lying for 30 minutes to collect the first reactive hyperemic response. To test the effect of preconditioning, the subject will then lie supine on the OR overlay for 40 minutes followed by side lying for 30 minutes for the second reactive hyperemic response.

Control protocol: The subject will first lie on his/her side quietly for 10 minutes to collect the baseline skin blood flow, followed by lying supine on the OR overlay (AliMed®) for 40 minutes, and then side lying for 30 minutes to collect the reactive hyperemic response for control protocol.

AP	Baseline (10 min)	AP overlay (40 min)	RH 1 (30 min)	OR overlay (40 min)	RH 2 (30 min)

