7.0 Expected Risks/Benefits

Expected Risks

Overall, potential risks associated with participation in the study are unlikely and of low risk. Subjects will be advised to speak with the PI if they believe they have been hurt by the study. Potential risks associated with the non-invasive protocols of our study are as followed:

- 1) Emotional stress: The risk of having emotional stress with our telephone screening procedure and examination of remaining sensation, motor and autonomic function is no more than minimal. Participants may feel uncomfortable answering personal health related questions. The examinations of remaining sensation, motor and autonomic function are regularly performed at the physician's office. Participants may feel uncomfortable that he or she could not feel or move the body below the level of injury. In addition, female subjects may feel added emotional stress if their screening pregnancy test results are positive and they were unaware that they were pregnant.
- 2) Discomfort: The risk of having discomfort with our heart rate, blood pressure, exams is no more than minimal. These examinations are regularly performed at the physician's office. Participants may feel discomfort caused by the blood pressure cuff and heart rate monitor belt.
- 3) Localized Ischemia: The risk of tissue ischemia associated with reactive hyperemia (caused by lying on OR or AP overlays) is low. Reactive

hyperemia is a normal physiological response induced by short-term non-damaging ischemia of the loaded area. The amount of pressure expected on sacrum and heels is very low (~60mmHg) and for a short period of time (40 minutes), which simulates the amount of pressure lying or sitting on a mattress or seat cushion. The amount, duration and area of localized pressure on the skin is within the current clinical practice guideline of pressure ulcer prevention, which is making turning the patient in bed every two hours. The skin breakdown risk associated with lying on OR or AP overlay is considered as rare (less than 1 out of 100 people).

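### The visit's first load follows only a 10-minute side-lying baseline, so effects of earlier loading may carry into it, and for Aim 3 random order would not cancel them

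*Combined protocol and SAP*

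**What the plan says.** Section 6.0 opens each protocol with a short rest that is also the baseline recording: "The subject will first lie on his/her side quietly for 10 minutes to collect the baseline skin blood flow". The 40-minute supine load follows directly.

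After each load the plan is more generous. In the AP protocol the AP load is followed by recovery, "and then side lying for 30 minutes to collect the first reactive hyperemic response", and the OR load is "followed by side lying for 30 minutes for the second reactive hyperemic response". The control load is treated alike: "and then side lying for 30 minutes to collect the reactive hyperemic response for control protocol". Between protocols, "A 30-minute washout period will be provided in between the two protocols"; posture and surface during that time are not given.

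Subjects are "not ambulatory and use a wheelchair for mobility" (section 4.1). Under section 5.0 they have about 30 minutes of face-to-face screening, with vital signs and motor, sensory and autonomic assessment, and then move on to the study procedures. Posture during screening is not described, and no settling period is mentioned. The risk text in section 7.0 describes the overlay load as one "which simulates the amount of pressure lying or sitting on a mattress or seat cushion".

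Section 12.0 plans paired t-tests on 15 subjects, with no period or sequence term. Aim 3 compares the OR load and RH2 of the AP protocol with the OR load and RH of the control protocol.

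**The concern.** Skin blood flow and reactive hyperaemia are sensitive to what the tissue has just been through; that is the premise of the study. The plan allows 30 minutes of recorded recovery after a 40-minute load and, between protocols, a further 30 minutes of washout. It applies no such standard to whatever loading or change of posture precedes the first baseline. Those first 10 minutes serve as both recovery and reference measurement.

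If something carries over, the loads being compared start from different states. For Aims 1 and 2 the difference follows the order of protocols, which is randomised. For Aim 3 it is tied to one side of the comparison. The control-first subjects matter most there, because only their control OR load is free of earlier AP exposure, and theirs is the control load that comes first in the visit. The pilot's results are also meant to size later studies (section 12.0), so avoidable noise would be passed on.

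**Working it through.** **1. The timetable against the stated duration.** Segments from section 6.0 and Figure 1:
- AP protocol: 10 + 40 + 30 + 40 + 30 = 150 min
- Control protocol: 10 + 40 + 30 = 80 min
- Washout: 30 min
- Total: 150 + 80 + 30 = 260 min = 4.33 h

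The plan states about 4.5 h (270 min), so the segments account for the stated time. The 10 minutes left over must also cover probe taping and transfers, which leaves little room for an unwritten rest.

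**2. Scheduled rest before each load.**
- First load of the visit: 10 min (the baseline).
- OR load after AP: 30 min (RH1).
- First load of the second protocol: 30 (RH or RH2) + 30 (washout) + 10 (baseline) = 70 min if the washout is unloaded; 10 min if it is spent loaded.

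With an unloaded washout:

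| Order | AP load | Control OR load | OR load after AP |
|---|---|---|---|
| AP first | 10 | 70 | 30 |
| Control first | 70 | 10 | 30 |

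**3. Aims 1 and 2.** Let d be the first-minus-second shift, in SDs of the paired difference (assumed; no value in the documents). It adds +d to AP minus control in AP-first subjects and −d in control-first subjects.
- Bias of the pooled mean = d × (AP-first − control-first)/15.
- Drawing 15 of the 20 envelopes gives 8:7 or 7:8 with probability 0.70, 9:6 or 6:9 with 0.27, and 10:5 or 5:10 with 0.03 (hypergeometric).
- The bias is therefore d/15 = 0.07d in size at 8:7 and 5d/15 = 0.33d at 10:5.
- The SD grows by about √(1 + d²), so 15 subjects carry the information of about 15/(1 + d²). At d = 0.25, 0.5 and 1.0 this is 14.1, 12.0 and 7.5. At d = 0 nothing is lost.

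**4. Aim 3.** Let C be the residual effect on an OR load that comes first in the visit (size and sign unknown). The OR load after AP starts at least 10 + 40 + 30 = 80 minutes into its protocol, so it is never first. Take the residual effect as gone by then, and the washout as unloaded.
- Control-first subjects: the paired difference (after AP minus control) shifts by −C.
- AP-first subjects: no shift.
- Pooled shift = −C × (control-first)/15. Its size is 5C/15 = C/3 to 10C/15 = 2C/3, and 0.47C or 0.53C at the likeliest splits.

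If the washout is instead spent under loading like that on arrival, every control OR load follows it by 10 minutes, and the shift becomes the full C.

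**5. With 30 minutes of settling added and an unloaded washout.** Rest becomes 10 + 30 = 40 min before the first load, 70 before the second protocol's first load, and 30 before the OR load after AP.

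**The case against.** Several counter-arguments stand:

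- **Carry-over is not shown.** Nothing in the documents says that sacral or heel blood flow needs more than 10 minutes to settle after sitting, or how far sitting loads those sites. The comparison with a seat cushion in section 7.0 is safety text about pressure magnitude. A reader might infer that the first baseline is contaminated; the documents support only that it may be.
- **Ten minutes is the scheduled minimum.** Posture in screening is not given, and taping probes to the sacrum and heel probably takes some time off the sacrum. Actual rest could be somewhat longer.
- **The 70 minutes is conditional.** A loaded washout removes the first-versus-second gap. It does not remove the Aim 3 imbalance, as step 4 shows.
- **Aims 1 and 2 are largely protected by random order.** A reader might infer systematic bias there; only a small one arises, and only if the orders are unequal. For interface pressure (Hypothesis 1) the documents suggest no mechanism by which earlier loading would matter.
- **Some difference in history is intended in Aim 3.** Prior AP loading is the preconditioning under test. Whatever preceded the subject's arrival is not part of it.
- **A settling period does not equalise rest.** With equal orders, mean rest before the control OR load rises from (10 + 70)/2 = 40 to (40 + 70)/2 = 55 minutes, against a fixed 30 after AP, so the mean gap widens from 10 to 25 minutes. The case for settling is that no load would follow a very short rest, not that intervals would match.

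**Conclusion.** The point holds as a possible source of noise and, for Aim 3, of one-sided bias. The 10/30/70-minute schedule follows from section 6.0, with 70 conditional on an unloaded washout. No settling time is stated before the first baseline, and the stated duration leaves little room for any. For Aims 1 and 2 the consequence is mainly variance. For Aim 3 a residual effect C would move the pooled mean by roughly C/2, or by all of C if the washout is spent under similar loading, and random order cannot cancel it.

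The size and direction of C and d are unknown and may be near zero, so the reduced-information figures are illustrative only. The documents do not support saying that the first baseline is invalid or that the Aim 3 result will be wrong. Arrival by wheelchair is inferred from section 4.1 and from the later transfer back to the chair in section 6.0. This is an inexpensive improvement to the procedure rather than a flaw that undermines the trial.

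**What to change.** In section 6.0, add a fixed settling period of side-lying, off the sacrum and heels, before the first protocol's 10-minute baseline; 30 minutes, for example, would match the plan's own washout. Tape the probes at its start so that the rest is quiet, and keep the Form E3 questions in screening, where section 5.0 places them. State that the washout is also spent side-lying, and record posture during screening.

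In section 12.0, add a period term to the Aims 1 and 2 comparisons. This removes the remaining order-linked shift without taking any participant time. It would not repair Aim 3, where the effect falls on one side only; the settling period is what helps there.

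The cost is a few sentences and up to 30 more minutes of visit, immobility and fasting. The listed parts of the visit now sum to 30 + 270 + 30 + 10 + 15 = 355 minutes, about 6 hours.

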7.0 Expected Risks/Benefits

Expected Risks

Overall, potential risks associated with participation in the study are unlikely and of low risk. Subjects will be advised to speak with the PI if they believe they have been hurt by the study. Potential risks associated with the non-invasive protocols of our study are as followed:

- 1) Emotional stress: The risk of having emotional stress with our telephone screening procedure and examination of remaining sensation, motor and autonomic function is no more than minimal. Participants may feel uncomfortable answering personal health related questions. The examinations of remaining sensation, motor and autonomic function are regularly performed at the physician's office. Participants may feel uncomfortable that he or she could not feel or move the body below the level of injury. In addition, female subjects may feel added emotional stress if their screening pregnancy test results are positive and they were unaware that they were pregnant.
- 2) Discomfort: The risk of having discomfort with our heart rate, blood pressure, exams is no more than minimal. These examinations are regularly performed at the physician's office. Participants may feel discomfort caused by the blood pressure cuff and heart rate monitor belt.
- 3) Localized Ischemia: The risk of tissue ischemia associated with reactive hyperemia (caused by lying on OR or AP overlays) is low. Reactive

hyperemia is a normal physiological response induced by short-term non-damaging ischemia of the loaded area. The amount of pressure expected on sacrum and heels is very low (~60mmHg) and for a short period of time (40 minutes), which simulates the amount of pressure lying or sitting on a mattress or seat cushion. The amount, duration and area of localized pressure on the skin is within the current clinical practice guideline of pressure ulcer prevention, which is making turning the patient in bed every two hours. The skin breakdown risk associated with lying on OR or AP overlay is considered as rare (less than 1 out of 100 people).

- 4) Localized Heating. The risk of burn associated with heat hyperemia is low. Heat hyperemia will be induced by short-term heating of the skin. The temperature of heating is very low (41°C or 106°F) and for a short period of time (5 minutes). This temperature and duration is far lower and shorter than the therapeutic hot packs used regularly in clinic (45-54°C) for more than 10 minutes covering the whole joint or lower back. Previous published literatures that investigated microcirculatory response in people with SCI induced heat hyperemia with 20-30 minutes heating at 41°C. No tissue burn or damage to the skin was noted in these published studies. The amount and duration of localized heating of the skin is far shorter than that causing burn of the skin. The skin breakdown risk associated with the heating protocol is considered as rare (less than 1 out of 100 people).
- 5) Electrical Stimulation. The risk of skin or muscle damage associated with electrical stimulation is low. The skin vasoconstrictor response will be induced using cutaneous electrical stimulation (3-10 mA, 0.2-1.0 ms pulses at 20 Hz, 1 s trains) delivered via 1 cm Ag-AgCl surface electrodes applied bilaterally (4 cm apart) to the forehead (above lesion) and the abdominal wall (below lesion). This is a standard protocol used to measure the sympathetic outflow of the microcirculatory response. The same protocol was used in previous studies on chronic spinal cord injury patients, and no damage to the skin or underlying muscle was noted. Electrical stimulation at a higher intensity and duration (10-50mA for 10 minutes) is one of the standard clinical practice protocol in nerve stimulation and pain reduction for patients with SCI. Therefore the skin or muscle damage associated with electrical stimulation is considered as rare (less than 1 out of 100 people).
- 6) Skin Blood Flow (SBF) and Tissue Oxygenation Testing will be performed using an FDA cleared non-invasive device. The amount of energy used with the laser light during the measurement is similar to that of a bar code scanner, and the white light is similar to that of ordinary daylight.
- 7) Bruising and swelling with venipuncture The risks of drawing blood from a vein includes discomfort at the site of the needle stick, possible bruising and swelling around the site of the needle stick is minimal. The risks of infection is very rare, and feeling faint from this procedure is uncommon.
- 8) Bare skin measurements. Bare skin measurements will be collected during this study. Some of the locations for the measurements, such as the sacrum

(low back) is very private, so the subject may feel embarrassed. A bed sheet will be provided to cover the subjects upon request.

9) **Breach of confidentiality.** The risk of breach of confidentiality is minimal since the only key to link subject ID and confidential information is locked in the file cabinet of the PI's locked office. The key will only be accessible to the PI's team. All other data is only coded with a subject ID in hard copy and electronic files. All hard copy files with subject ID only will be stored in a locked cabinet in the PI's locked laboratory, which is three floors away from the PI's office. All electronic data do not contain any confidential information, and they will be stored on the laptop used to collect data, and the hard drive located in the PI's Laboratory. Both computers are password protected, and the data are only accessible to the PI's team. All study personnel are trained in the maintenance of security and confidentiality of research data.

Benefits.

There is no direct benefit for the participants in this study, however findings from these participants will help us understand the potential benefit of the Dabir AP overlay as compared to the regular OR overlay, and the potential use of Dabir AP overlay on ischemia-preconditioning.

8.0 Data Collection and Management Procedures

Three sets of data (and one biological sample) will be collected from the subjects. The following listed the details of data procurement, storage, and encryption: All data will be stored at UIC, and data will not be shared or stored at Schwab.

- 1) Confidential information (hard copy only): Confidential information that includes direct identifiers such as name, date of birth and phone number will be recorded on **Form A**. A subject ID (code) will be assigned to the subject by PI upon study enrollment for the purpose of protecting the confidentiality of the subject data for analysis purpose. Form A will serve as the key to the code. **Form G** is the compensation form. Participants will be asked to sign the form once the payment is received. Form A and G will be stored in a locked file cabinet in PI's locked office (UIC Applied Health Science Building, Rm 506H). Only the PI will have access to this locked file cabinet. A portable lock cash box will be used to transport Form A and G between the DHSP building and Department of Physical Therapy. Form A and G will be stored up to five years and destroyed afterwards so that all data will be de-identified for future analyses only.
- 2) Paper-based data (hard copy and excel spread sheet) will be coded using the subject ID on forms: B, C, D, E and F. These forms will be stored in a locked file cabinet in PI's locked laboratory (UIC Applied Health Science Building, Rm 272; different from the room that stores Forms A and G). The PI's team will be responsible for incorporating data on these forms to an excel

spreadsheet for further statistical analyses. Two layers of encryption will be used to ensure the security of excel file. These coded data will be stored up to seven years after completion of this study.

- 3) Skin blood flow data (electronic text file generated automatically with data acquisition system): Skin blood flow data will be collected directly via the LDF. These analog signals are automatically stored on the UIC laptop used for data collection. Only [name] team can log on to the password protection laptop to collect and access the blood flow and tissue oxygenation data. The assigned subject ID will be the only identifier of the data set collected from each subject. These coded data will be stored up to seven years after completion of this study.
- 4) Blood sample: The blood samples not used to probe for blood glucose and lipid profile will be stored coded at co-investigator [name] lab (UIC Applied Health Science Building, Rm 106). [name] will not have access to the key of the code.
- 5) Urine sample: Urine will be collected from women of childbearing age for pregnancy testing during visit one for eligibility screening. Any urine remaining after the testing will be disposed of.

9.0 Data Analysis

The MatLab program (The MathWorks Natick, MA) will be used to process the skin blood flow signal. The signals will be analyzed with two signal processing methods to characterize the responses in both time and frequency domains. Details of both methods were published previously by the PI.¹⁴

1) *Exponential curve-fitting technique:*

To select the time-domain parameters of the reactive hyperemia and heat hyperemia objectively. A tenth ordered Chebyshev I low pass filter (with cut off frequency at 0.15 Hz) will be applied to remove the noise caused by respiration and cardiac movement.¹⁰ We will use a least squares model to fit the filtered reactive and heat hyperemic curves, and all parameters (including peak, time to peak, area under curve of reactive hyperemia; and first peak, second peak and time to first and second peaks, area under curve of heat hyperemia) will be derived from the fit curves.

2) *Time-frequency analysis:*

To further examine the different control mechanisms of SBF by decomposing the signal in frequency domain. Short-time Fourier transform will be used to decompose the signal by breaking the signal into short-time segments (windows), then computed Fourier analysis within each segment to calculate

spectral densities. A 256-sample Hanning window (512 seconds) will be used to compute the spectrogram.

Please see section 12.0 for details of all statistical analyses.

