10.0 Quality Control and Quality Assurance

[name] will be responsible for quality control and quality assurance of the data collected. [name] has more than ten years of experiences in pressure ulcer research using non-invasive blood flow measurements, and she will perform the protocols in person and shadow her research team on the first two subjects. [name] will then supervise the data collection on site for the next three subjects recruited in this study. [name] will check all the data within two days of collection (paper and electronic formats). If the study team encounter any issues related to data collection, [name] is available through phone calls to address the concerns. [name] will meet with her team every two weeks to check the laboratory notes and monitor the study regularly.

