12.0 Statistical Considerations

For aims 1 and 2, paired *t*-tests will be computed to compare the interface pressure and skin blood flow during 40 minutes of AP overlay (AP protocol) vs. OR overlay (Ctrl protocol). Paired *t*-tests will also be used to compare the reactive hyperemic response during RH1 (AP protocol) vs. RH (Ctrl protocol). For aim 3, paired *t*-tests will be computed to compare the skin blood flow during OR overlay (AP protocol) vs. OR overlay (Ctrl protocol), and the reactive hyperemic response during RH2 (AP protocol) vs. RH (Ctrl protocol). SPSS will be used for all statistical analyses. Since this is a pilot study, we will test the study on 15 subjects. Results from this study will be used to calculate sample size for future studies. In case of dropout or subject decease during this study, we propose to recruit up to 20 subjects for this study.

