Sensation of need for a bowel movement	
Ability to Prevent Stool Leakage (continence)	
Voluntary sphincter contraction	
Sexual Function	
Genital arousal (erection or lubrication)	Psychogenic
	Reflex
Orgasm	
Ejaculation (male only)	
Sensation of Menses (female only)	

2=Normal function, 1=Reduced or Altered Neurological Function
 0=Complete loss of control, NT=Unable to assess due to preexisting or concomitant problems

Date of Injury _____ Date of Assessment _____

This form may be freely copied and reproduced but not modified.
 This assessment should use the terminology found in the International SCI Data Sets (ASIA and ISCoS - <http://www.iscos.org.uk>)

Examiner _____

Dabir AP Overlay (PI: [name]): Alternating Pressure Overlay on Weight Bearing Tissue Tolerance in SCI
Research Data Collection Forms
Subject ID: _____

FORM F – TEST DATA

Envelope A: CTRL → AP

Session	Heart Rate		Blood Pressure	
	Before	After	Before	After
CTRL				
AP				

Envelope B: AP → CTRL

Session	Heart Rate		Blood Pressure	
	Before	After	Before	After
AP				
CTRL				

(Signature of Investigator)

(Date)

Dabir AP Overlay (PI: [name]): Alternating Pressure Overlay on Weight Bearing Tissue Tolerance in SCI
Research Data Collection Forms
Subject ID: _____

FORM G – COMPENSATION

I, _____, acknowledge that I am to receive compensation for participating in this study \$_____ on ____/____/____.

Participant's signature _____ Date _____

Researcher's signature _____ Date _____

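### Section 9.0 specifies no masking for processing the reactive hyperaemia recordings, so nothing prevents fitting decisions from being made with the protocol (AP or control) known

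*Combined protocol and SAP*

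**What the plan says.** Section 9.0 sets a tenth-order Chebyshev I low-pass filter with a 0.15 Hz cut-off and continues: "We will use a least squares model to fit the filtered reactive and heat hyperemic curves". Every reactive hyperaemia parameter (peak, time to peak, area under the curve) is derived from the fitted curve. The stated aim is objective selection, and details of the method are left to an earlier publication by the investigator.

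Section 6.0 gives three reactive hyperaemia recordings per subject at two sites, sacrum and one heel. In the AP protocol the subject lies on the AP overlay, "then side lying for 30 minutes to collect the first reactive hyperemic response" (RH1), then lies on the OR overlay and side-lies for another 30 minutes (RH2). The control protocol has one OR overlay period followed by 30 minutes of side lying (RH).

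On people and files:
- Section 8.0 gives access to the flow data only to the investigator's team and labels the data sets by subject ID. The same team transfers Forms B to F into the analysis spreadsheet.
- Form F in the appendices records the order, for example "Envelope B: AP → CTRL".
- Under section 10.0 the responsible investigator performs the protocols for the first two subjects, supervises the next three on site, and checks all paper and electronic data within two days of collection.

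Section 12.0 compares RH1 with control RH, and RH2 with control RH, by paired t-tests.

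**The concern.** The overlays cannot be hidden at the bedside, but the hyperaemia recordings can be masked afterwards, and the plan does not use this. Hypotheses 1b and 3 both predict a smaller response after AP. If onset, fit window, artefact removal or the handling of a poor fit differs between conditions, even unintentionally, the difference passes into the fitted parameters and then into the paired difference. A paired t-test cannot separate such a shift from an effect of the overlay, and a reader of this device comparison could not rule it out. Section 12.0 adds: "Results from this study will be used to calculate sample size for future studies". A biased effect would therefore carry forward into later planning.

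**Working it through.** **1. The plan's own figure.** Section 12.0 says "Since this is a pilot study, we will test the study on 15 subjects" and, to allow for dropout, "we propose to recruit up to 20 subjects for this study". No alpha, power, effect size or SD is given, so there is no power calculation to reproduce. The step from 15 to 20 equals an unstated 25% dropout: 15 / (1 − 0.25) = 20.

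**2. Who could know the condition.**

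| Question | What the documents give |
|---|---|
| Who fits the curves? | The study team, in the first person plural (9.0); no separate analyst |
| Who can open the flow files? | Only the investigator's team (8.0) |
| What does the file label hide? | The person (subject ID), not the overlay or order (8.0) |
| Who handles the order? | The same team, through Form F (8.0, appendices) |
| Is anyone masked? | No step for operator, checker, curve fitter or statistician |

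This supports the statement that nothing prevents unmasked processing. It does not show that the fitter knows the condition.

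**3. What is fixed and what is open.** Fixed: filter type, order and cut-off; least squares; derivation from the fitted curve. Not written in the plan: the onset rule, fit window, exact model form, baseline reference, artefact rule and failed-fit rule. The probes are taped on throughout, and the subject moves from supine to side lying just as hyperaemia begins, so movement artefact at that point is plausible, although the documents do not mention it. A 0.15 Hz cut-off passes changes slower than about 1 / 0.15 = 6.7 s, so the filter alone cannot be relied on to remove it.

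**4. Whether masking is feasible.** RH1, RH2 and control RH are all 30-minute side-lying recordings off the overlay, stored electronically. RH2 and control RH both follow 40 minutes on the OR overlay, so that pair can be masked best. The full AP recording shows two loading periods and the AP cycle, so the segments must be cut out first. Number of curves: 15 × 3 × 2 = 90, or 20 × 3 × 2 = 120.

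**5. What a shift would do (illustration).** Assume two-sided alpha 0.05, no true effect, and a shift of b SDs of the paired difference toward AP. The chance of a significant result favouring AP is P(T > t crit), where T is noncentral t with n − 1 degrees of freedom and noncentrality b√n. The critical value is 2.145 at n = 15 and 2.093 at n = 20.

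| b (assumed) | n = 15 | n = 20 |
|---|---|---|
| 0 | 2.5% | 2.5% |
| 0.1 | 5.5% | 6.2% |
| 0.2 | 10.8% | 13.4% |
| 0.3 | 19.0% | 24.7% |
| 0.5 | 43.8% | 56.5% |

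The documents give no value for b.

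**6. Whether onset placement matters.** Because section 9.0 lists time to peak, the curve must rise before it falls. I fitted A(exp(−t/d) − exp(−t/r)) to noise-free 30-minute curves, with assumed rise constants r of 5 to 30 s and decay constants d of 60 to 300 s. Starting the fit 10 s late raised the fitted peak by about 4% to 12%. Starting 10 s early lowered it by about 4% to 17%. Onset choice therefore matters, but the direction depends on the error.

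**The case against.** The strongest defence is that the processing is largely mechanical. The filter is set in advance, the fit is least squares, every parameter comes from the fitted curve, and the cited publication may fix or automate the remaining choices. This stands as a limit on size. That publication is not available here, and by its title it is a local-cooling study, so it cannot say who is masked to the overlay in this trial.

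Four stronger readings are tempting, and the documents do not support them:

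- **That the curves are fitted with the overlay known.** No sentence names the fitter or says what that person knows. It is an inference from the wording, team-only access and the absence of masking.
- **That an analyst makes manual choices curve by curve.** The plan leaves the rules unwritten; it does not describe them as manual.
- **That the lead investigator runs every session, or that the two-day check is a route for bias.** Section 10.0 has that person perform or supervise only the first five subjects (2 + 3). The check, by which that investigator "will check all the data within two days of collection (paper and electronic formats", is a data-quality step, and nothing says that curves are fitted or excluded there.
- **That late onset lowers the fitted peak by a calculable amount.** This assumes pure decay from release, which does not fit a plan that measures time to peak. Under a rise-and-decay curve a late start raises the peak. Nothing in the documents suggests a consistent timing difference between conditions.

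It is also fair that this is a pilot. That lowers the stakes but does not justify leaving out a nearly free safeguard.

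**Conclusion.** The concern holds in limited form. Section 9.0 specifies no masking for processing RH1, RH2 and control RH, and the only people with access are the team that runs the sessions and enters Form F. Bias toward the smaller response of Hypotheses 1b and 3 is possible, not shown, and of unknown size. The false-positive figures rest on assumed shifts, and the onset figures on an assumed curve shape; neither estimates what will happen in this trial. The change should be made because masking is feasible and cheap here, not because bias has been demonstrated. Sample size is unaffected.

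**What to change.** Add to section 9.0:

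1. A script cuts RH1, RH2 and control RH at each site into separate files with random codes and no date, clock time, protocol or order.
2. Rules for onset, fit window, model form, artefacts and failed fits are written beforehand and applied to the coded files.
3. Parameters are locked before the codes are linked to Form F for the section 12.0 tests.
4. Any baseline normalisation is applied by script after locking, because RH1 and RH2 share one baseline and that could reveal the pairing.
5. The two-day check stays as it is, so that probe failure is still caught early, but no curve is fitted or excluded at that check.
6. Flow and pressure under load are stated to be processed unmasked, since the AP cycle is visible. Masking is stated to be strongest for the Aim 3 pair (RH2 against control RH), since a real overlay effect could partly unmask RH1.

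Cost: one relabelling script, the added text and rules in section 9.0, and a short delay before results can be seen by condition. No extra staff, visits or procedures are needed.
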